12.0 Descriptive Factors

- 12.1 Phase I only: Dose level (as assigned by registration office): -2 vs. -1 vs. 1 vs. 2
- 12.2 International Prognostic Index (IPI) [Shipp et al, 1993]: low risk (0 or 1 risk factors) vs. low intermediate (2 risk factors) vs. high intermediate (3 risk factors) vs. high (4 or 5 risk factors)

Risk Factors	0 points	1 point
Age	≤ 60 yrs.	> 60 yrs.
Serum LDH	≤ 1 x normal	> 1 x normal
ECOG PS	0 or 1	≥ 2
Stage	I or II	III or IV
Extranodal involvement	≤ 1 site	> 1 site

Total number of risk factors = sum of the number of points for each prognostic factor.

13.0 Treatment/Follow-up Decision at Evaluation of Patient

- 13.1 Patients who are CMR, PMR, or NMR will continue treatment per protocol for 2 cycles. The patient may receive a 3rd and 4th cycle of treatment per MD discretion.
- 13.2 Patients who develop PMD while receiving therapy will go to the event-monitoring phase.
- 13.3 Patients who go off protocol treatment for reasons other than PMD will go to the event-monitoring phase per Section 18.0.

- 13.4 Phase I Only: If a patient fails to complete the first cycle of treatment for reasons other than toxicity, the patient will be regarded as not evaluable and will be replaced.
- 13.5 A patient is deemed *ineligible* if after registration, it is determined that at the time of registration, the patient did not satisfy each and every eligibility criteria for study entry. The patient may continue treatment off-protocol at the discretion of the physician as long as there are no safety concerns, and the patient was properly registered. The patient will go directly to the event-monitoring phase of the study (or off study, if applicable).
- If the patient received treatment, all data up until the point of confirmation of ineligibility must be submitted. Event monitoring will be required per Section 18.0 of the protocol.
 - If the patient never received treatment, on-study material and the End of Active Treatment/Cancel Notification Form must be submitted. No further data submission is necessary.
- 13.6 A patient is deemed a *major violation*, if protocol requirements regarding treatment in cycle 1 of the initial therapy are severely violated that evaluability for primary end point is questionable. All data up until the point of confirmation of a major violation must be submitted. The patient will go directly to the event-monitoring phase of the study. The patient may continue treatment off-protocol at the discretion of the physician as long as there are no safety concerns, and the patient was properly registered. Event monitoring will be required per Section 18.0 of the protocol.
- 13.7 A patient is deemed a *cancel* if he/she is removed from the study for any reason before any study treatment is given. On-study material and the End of Active Treatment/Cancel Notification Form must be submitted. No further data submission is necessary.

14.0 Body Fluid Biospecimens

14.1 Body Fluid Biospecimen Submission

14.11 Summary Table of Body Fluid Biospecimens for This Protocol

Type of biospecimen to submit	Mandatory or optional	When to submit	Reason for submission (background/ methodology section)	Where to find specific details for specimen submission
Blood/blood products	Mandatory	Serial Draws	Correlative Studies (Section 14.31)	Section 14.2

14.2 Blood/Blood Products Handling

14.21 Kits are required for this study.

- 14.211 The kit contains supplies and instructions for collecting, processing, and shipping specimens.

- 14.212 Participating institutions may obtain kits by completing and faxing the Supply Order Form (found in the Forms Packet) to the number listed on the form. Fill out the site address to where the kits will be shipped on the fax supply form. Because we are now being charged for all outgoing kits, a small, but sufficient, supply of the specimen collection kits should be ordered prior to patient entry. Do not send unused kits back to BAP.
- 14.213 Kits will be sent via FedEx® Ground at no additional cost to the participating institutions. **Allow at least two weeks to receive the kits.**
- 14.214 Kits will not be sent via rush delivery service unless the participating institution provides their own FedEx® account number or alternate billing number for express service. **ACCRU will not cover the cost for rush delivery of kits.**
- 14.22 All samples must be collected **Monday-Thursday ONLY.**
- 14.23 Label specimen tubes with protocol number, ACCRU patient ID number, and time and date blood drawn.

14.24 Collect and process all blood/blood products according to specific kit instructions and table below.

Mandatory	Collection tube description and/or additive (color of tube top)	Volume to collect per tube (number of tubes to be collected)	Blood product being processed and submitted by participating site	After registration, but prior to treatment Cycle 1 Day 1	Cycle 1 Day 2	Cycle 1 Day3	At restaging after cycle 2, i.e. at time of PET scan/end of treatment	Additional processing required at site after blood draw?	Storage/ shipping conditions ¹
Mandatory	ACD (yellow)	10 ml (1)	Whole Blood	X			X	No	Refrigerate/c old pack (DO NOT FREEZE)
Mandatory	EDTA* (purple)	10 ml (1)	Whole Blood	X			X	No	Refrigerate/c old pack (DO NOT FREEZE)
Mandatory	EDTA* (purple)	10 ml (1)	Whole Blood	X	X	X	X	No	Refrigerate/c old pack (DO NOT FREEZE)
Mandatory	None (red)	10mL(1)	Whole Blood	X			X	No	Refrigerate/c old pack (DO NOT FREEZE)
Total (100 cc)				40 cc	10 cc	10 cc	40 cc		

¹ After all samples have been collected according to kit instructions, ship all specimens according to shipping instructions (see Section 14.25 for detailed shipping instructions.)

14.25 Shipping

14.251 Verify ALL sections of the Blood Specimen Submission Form (see Forms Packet), Mayo Medical Laboratories (BAP) Requisition Form (provided in kit), and specimen collection labels are completed and filled in correctly. Enter information from the Blood Specimen Submission

- 14.252 Specimens must be shipped the same day they are drawn.
- 14.253 Ship ACD, EDTA, and no additive (red top) whole blood tubes with a properly prepared cold pack. See kit instructions for specific details for cold pack preparation (i.e., frozen or refrigerated) and proper packing of blood and cold pack to avoid freezing of specimen.
- 14.254 Ship specimens via Priority Overnight service, **Monday – Thursday ONLY**, to Mayo Foundation, [REDACTED] **Do not collect or send samples the day before, the day of, or the observed day of a national holiday. Friday Shipments are allowed as long as the shipment is marked for Saturday delivery.**
- 14.255 The BAP kits will contain a smart shipper label (white barcoded label) affixed to the white colored shipping boxes. The smart shipper label is a pre-addressed return label, which replaces the need for an airbill. Shipping costs will be covered by ACCRU if this brown colored box is used for shipping specimens to Mayo Foundation [REDACTED] [REDACTED]

14.3 Study Methodology and Storage Information

Collection tube description and/or additive (color of tube top)	Component Available	Minimal Residual Disease assessment (MRD)	Cell Surface Markers (Flow Cytometry)	DNA (SNPs)	RNA	Western blotting	Cytokines
ACD (yellow)	Mononuclear cells (from Ficoll)		X (preferred)	X	X	X	
EDTA (purple)	Plasma	X					X
EDTA (purple)	Buffy coat		X	X (preferred)		X	
None (red)	Serum						X
EDTA	Whole Blood	X					

14.31 Blood/blood product samples will be collected for protocol specific research. The following paragraphs offer descriptions of current assays being run on lymphoma trials. These may vary by protocol.

14.311 **Serum free light chains:** Serum will be processed from the red top tube and will be frozen, batched, and analyzed for serum free light chains in [redacted] research laboratory, [redacted]. In a recent publication by Martin et al (Translational Research 149(4): 231 - 235, 2007) 36% of patients with mantle cell lymphoma had positive serology for serum free light chains. In this study we will assay for serum free light chains at on study and after two cycles of treatment. All samples will be evaluated with the Freelite serum free light chain assay (The Binding Site, Birmingham, UK). This is a commercial assay run routinely in [redacted] laboratory.

14.312 **Single nucleotide polymorphisms (SNPs) in host immune genes:** Buffy coat will be isolated in the Laboratory of [redacted] for future genomic DNA. We have previously demonstrated our

ability to analyze SNPs in patients with lymphoma. For example, Cerhan et al. (Blood 109: 5439 - 46) demonstrated that host gene SNP profiles could predict prognosis in follicular lymphoma. This information is not yet available for mantle cell lymphoma; therefore we will study that in this protocol. Genomic DNA samples will be batched and analyzed in the Mayo Clinic Cancer Center Genotyping Shared Resource.

14.313 **Vitamin D metabolites:** Serum from the red top tube will be cryopreserved and batched for 25 hydroxy vitamin D levels. These will be studied in the laboratory of [name]., Ph.D., Mayo Clinic Rochester, by liquid chromatography/tandem mass spectrometry. The rationale to study vitamin D in lymphoma comes from the finding that lymphoma is more common in climates with less sunshine. A recent study in the Journal of Clinical Oncology (26:2984 - 2991, 2008) demonstrated a significant improvement in overall survival in colon cancer patients with a higher level of vitamin D.

14.314 **Serum Cytokines:** Thirty cytokines, including pro-inflammatory, Th1 and Th2 associated cytokines, will be analyzed for each time point. The cytokines to be analyzed are IL-1 β , IL-1RA, IL-2, IL-2R, IL-4, IL-5, IL-6, IL-7, IL-8, IL-10, IL-12p40/p70, IL-13, IL-15, IL-17, TNF- α , IFN- α , IFN- γ , GM-CSF, MIP-1 α , MIP-1 β , IP-10, MIG, Eotaxin, RANTES, MCP-1, VEGF, G-CSF, EGF, FGF-basic, and HGF. Assays will be run in triplicate according to the manufacturers' protocol. Data will be collected using the Luminex-100 system Version 1.7 (Luminex, Austin, TX) available in our lab at the research base. Data analysis will be performed using the MasterPlex QT 1.0 system (MiraiBio, Alameda, CA). A five-parameter regression formula will be used to calculate the sample concentrations from the standard curves and a change of 50% from the baseline value will be considered significant.

14.315 **Flow cytometry:** 1×10^6 cells will be washed in phosphate-buffered saline (PBS) containing 0.5% bovine serum albumin (BSA), incubated with specific antibodies to the marker in question and analyzed on a FACSCalibur flow cytometry (Becton-Dickinson). Isotype controls will be done for each sample.

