 - 9 Slides should be submitted ≤ 30 days of enrollment, as instructed in Section 17. Central pathology review is required, but is retrospective and will not prohibit enrollment into the study.
 - 10 Correlative research blood collected prior to treatment Cycle 1 Day 1, Cycle 1 Day 2, Cycle 1 Day 3 and Cycle 2 Day 21 (see Section 14.0).
 - 11 Follow-up period is every 3 months for years 1 to 3, then yearly in years 4 and 5.
- R Research funded (see Section 19.0; patients must be willing to submit mandatory blood samples as outlined in Section 14.0).

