8.0 Dosage Modification Based on Adverse Events

Dose adjustments of ICE chemotherapy are to be performed per institutional standards. All patients will receive prophylactic hematopoietic growth factors (e.g., granulocyte-colony stimulating factor [G-CSF]) to shorten the period of neutropenia and transfusions of blood products should be provided during the course of treatment per institutional guidelines.

Standard practice and local prescribing information will be followed for rituximab and background chemotherapy. Omitting or discontinuing background therapy must lead to omitting or discontinuing of lenalidomide as well.

Dose Modifications at the start of next treatment cycles:

Dose modifications of Lenalidomide will be based on the dose levels as noted in Table 8.1 and on adverse events noted during preceding cycles (see Table 8.2 for guidance regarding dose reductions based on adverse events).

Dose modifications during a treatment cycle:

Please note, while patient is actively on Lenalidomide, modifications are not allowed during the particular treatment cycle and are only allowed Day 1 of any particular cycle. Decreasing by one dose level would be for the next cycle of treatment. During active treatment cycle, treatment can be held for up to 7 days if needed.

If multiple adverse events are seen, administer dose based on greatest reduction required for any single adverse event observed. Reductions apply to treatment given in the preceding cycle and are based on adverse events observed since the prior dose.

ALERT: ADR reporting may be required for some adverse events (See Section 10)

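### Section 14.314 calls any 50% change in each of 30 cytokines significant, with no link to variability or multiplicity, and the specimen type per time point is not fixed

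*Combined protocol and SAP*

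**What the plan says.** Section 14.314, headed as serum cytokines, states: "Thirty cytokines, including pro-inflammatory, Th1 and Th2 associated cytokines, will be analyzed for each time point". It lists the analytes, G-CSF among them, says "Assays will be run in triplicate according to the manufacturers' protocol", and closes with the rule that "a change of 50% from the baseline value will be considered significant". It gives no test, error rate, direction, CV or multiplicity rule.

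On sampling, footnote 10 of the test schedule has "Correlative research blood collected prior to treatment Cycle 1 Day 1, Cycle 1 Day 2, Cycle 1 Day 3 and Cycle 2 Day 21". In the collection table of 14.24 the red-top (serum) tube is marked only before Cycle 1 Day 1 and at restaging after cycle 2. Cycle 1 Day 2 and Day 3 (C1D2 and C1D3) have a single EDTA tube each. The table in 14.3 marks both EDTA plasma and red-top serum as usable for cytokines and does not assign either to a time point. For another serum assay, in 14.311, the times are spelled out: "we will assay for serum free light chains at on study and after two cycles of treatment".

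Section 8.0 adds that "All patients will receive prophylactic hematopoietic growth factors". Sections 7.11 and 7.12 schedule pegfilgrastim on Day 4.

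**The concern.** A fixed percentage change says nothing about whether the change exceeds what the assay and ordinary within-patient fluctuation produce. Applied to 30 analytes in every patient, with up to three post-baseline samples, it can flag many cytokines where nothing has changed. Because 50% up and 50% down are not equidistant on a ratio scale, noise alone produces more apparent rises than falls. Phase II has one arm, so no control group shows how often the rule fires without lenalidomide.

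The specimen question is separate. If the specimen type is not fixed, a change from baseline could mix serum with plasma, and no later analysis can remove that. One analyte also has a known outside source: G-CSF measured after growth factor has been given may reflect the administered product.

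**Working it through.** **1. Is serum available at every draw?** Inputs are the 10 mL tubes in 14.24. One ACD, one EDTA and one red-top tube are drawn at baseline and after cycle 2; a second EDTA tube is drawn at all four times.

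- Baseline: 4 × 10 = 40 cc
- C1D2: 1 × 10 = 10 cc
- C1D3: 1 × 10 = 10 cc
- After cycle 2: 4 × 10 = 40 cc
- Total: 40 + 10 + 10 + 40 = 100 cc, which matches the stated total.

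A red-top tube on C1D2 and C1D3 would give 40 + 20 + 20 + 40 = 120 cc. The stated volume therefore confirms that no serum tube is drawn on those two days.

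**2. How often does the 50% rule fire when nothing has changed?** There is no stated error rate to reproduce, and the CV is an assumption. Take log-normal values, independent errors at baseline and follow-up, and a total within-patient CV (assay plus biological) that is the same at both visits.

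- SD of log(post/baseline): s = √(2 × ln(1 + CV²))
- False rise: P(ratio ≥ 1.5) = 1 − Φ(ln 1.5 / s)
- False fall: P(ratio ≤ 0.5) = Φ(ln 0.5 / s)

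Worked example at CV 30%: s = √(2 × ln 1.09) = √(2 × 0.0862) = 0.415. Rise: 0.405/0.415 = 0.977, giving 0.1644. Fall: 0.693/0.415 = 1.670, giving 0.0475. The sum is 0.2119, and 30 × 0.2119 = 6.4.

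| Assumed CV | s | False rise | False fall | Either | Expected of 30 | At least one of 30 |
|---|---|---|---|---|---|---|
| 10% | 0.141 | 0.0020 | <0.0001 | 0.0020 | 0.06 | 0.06 |
| 15% | 0.211 | 0.0273 | 0.0005 | 0.0278 | 0.8 | 0.57 |
| 20% | 0.280 | 0.0738 | 0.0067 | 0.0805 | 2.4 | 0.92 |
| 30% | 0.415 | 0.1644 | 0.0475 | 0.2119 | 6.4 | 0.999 |
| 40% | 0.545 | 0.2284 | 0.1016 | 0.3300 | 9.9 | >0.999 |

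All figures are per patient per follow-up time. The last column, 1 − (1 − p)^30, also assumes independent analytes; the expected counts do not.

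**3. Which samples does growth factor touch?** With pegfilgrastim scheduled on Day 4, C1D2 and C1D3 precede it within the cycle. Only the sample after cycle 2 follows it.

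**The case against.** The strongest reply is that this is generic laboratory text. Section 14.31 introduces the assay paragraphs with "The following paragraphs offer descriptions of current assays being run on lymphoma trials. These may vary by protocol", and two neighbouring paragraphs still speak of mantle cell lymphoma. Cytokines are named in none of the correlative goals (2.31 to 2.34) and nowhere in 16.43. Section 16.436 plans only descriptive summaries of stored-serum work, and 16.23 calls phase I laboratory correlates exploratory. The word significant carries no p-value and may be meant as a laboratory threshold. Triplicates reduce assay error, and at a CV of 10% the rule rarely misfires. The flags are also per patient: under the model above the cohort's median ratio stays at 1.

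Much of this stands and limits the weight of the point, but it does not remove the rule. Section 14.11 gives 14.31 as the reason for the mandatory blood, 14.314 is the only cytokine rule in the documents, and 16.436 neither names cytokines nor withdraws the word. Triplicates do not reduce biological variation. That the cohort median is undisturbed is an argument for a paired cohort analysis in place of per-patient flags.

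Four stronger readings are tempting and not supported:

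- **The plan requires serum at all four draws.** It does not say so. Section 14.3 also allows EDTA plasma, and the phrase about time points may mean the two serum draws, as for free light chains.
- **A serum-to-plasma switch is planned.** No section plans one, and EDTA blood is also drawn at baseline. The gap is that the specimen type is left open.
- **Noise will be reported as a drug effect.** No section commits to reporting a 50% change that way.
- **The post-cycle-2 sample always falls seven days after the last lenalidomide dose.** Dose level −2 runs for 10 days, and the reductions in 8.1 reach days 1 to 7.

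**Conclusion.** The point holds as a minor one about analysis choice and internal consistency. The 50% rule is uncalibrated, has no multiplicity control, and sets unequal thresholds for rises and falls. With no true change its false-flag rate runs from 0.2% of analytes at a CV of 10% to 33% at 40%. At 30%, false rises outnumber false falls by 16.4% to about 4.7%. These sizes rest on log-normality, independent errors between visits and a CV that the documents do not give, so the problem is negligible if the total CV is near 10% and substantial from about 20% upwards.

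Sections 14.314, 14.24 and 14.3 also do not fit together on which specimen is used when. The primary endpoint, the interim and final decision rules and the stated secondary endpoints are untouched.

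**What to change.** 1. In 14.314, replace the 50% significance rule with an exploratory paired analysis of log(post/baseline) for each cytokine, for example Wilcoxon signed-rank, with false discovery rate control across the 30 analytes at each time point. Keep the 50% change, if at all, only as a descriptive threshold.
2. Reconcile 14.314, 14.24 and 14.3 so that each comparison uses the same specimen type at baseline and follow-up. Use serum for baseline against post-cycle 2. Use EDTA plasma for C1D2 and C1D3 only if the tube drawn on those days can supply it. This needs checking: 14.24 has two EDTA rows, only one of them is drawn on those days, and 14.3 also assigns EDTA blood to the minimal residual disease assay.
3. Flag G-CSF values measured after growth factor is given.

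The cost is mainly wording, with no extra blood if plasma is available at all four times. If it is not, C1D2 and C1D3 drop out of the cytokine comparison. The downside is that fewer cytokines will be reported as changed. Settle the specimen type before samples are batched, because analysis cannot correct it afterwards.

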14.4 Return of Genetic Testing Research Results

Because the results generated by the genetic testing included in this section are not currently anticipated to have clinical relevance to the patient or their family members, the genetic results will not be disclosed to the patients or their physicians.

If at any time, genetic results are obtained that may have clinical relevance, IRB review and approval will be sought regarding the most appropriate manner of disclosure and whether or not validation in a CLIA-certified setting will be required. Sharing of research data with individual patients should only occur when data have been validated by multiple studies and testing has been done in CLIA-approved laboratories.

15.0 Drug Information

15.1 Lenalidomide (Revlimid®, CC-5013, CDC-501) – IND number 060100

The most current version of the Investigator Brochure will be maintained in the study folder on the ACCRU website. Updated Investigator's Brochures should be obtained from the study folder as they become available.

Each investigator should obtain a copy of the Investigator's Brochure prior to initiation of the study.

Please consult the most current Investigator's Brochure and package insert for complete drug information.

15.11 **Background:** Lenalidomide has a wide range of effects, including the inhibition of hematopoietic tumor cell proliferation, the enhancement of T cells and natural killer (NK) cell activity, the modulation of stem cell differentiation, the inhibition of angiogenesis, and the inhibition of inflammation.

15.12 **Formulation:** For clinical study, lenalidomide is provided as 1.25-, 2.5-, 5-, 10-, 15-, 20-, and 25-mg capsules for oral administration. Each capsule contains lenalidomide as the active ingredient and the following inactive ingredients: anhydrous lactose, microcrystalline cellulose, croscarmellose sodium, and magnesium stearate.

The lenalidomide capsules are supplied in push-through blister foil or tamper-evident, child-resistant, opaque, high-density polyethylene (HDPE) containers with HDPE caps.

15.13 **Preparation and storage:** Lenalidomide should be stored at room temperature, between 59 and 86°F (15-30°C). Store drug away from direct sunlight.

15.14 **Administration:** Capsules are administered by mouth daily with water. Patients should not break, chew or open the capsules.

15.15 **Pharmacokinetic information:**

a) Absorption – Lenalidomide is rapidly absorbed following oral administration to subjects with multiple myeloma or MDS, with maximum plasma concentrations occurring between 0.5 and 1.5 hours post-dose. Co-administration with a high-fat and high-calorie meal in healthy subjects reduced the extent of absorption, resulting in an approximately 20% decrease in AUC and 50% decrease in C_{max} in plasma.

In the pivotal MM and MDS registration trials where the efficacy and safety were established for lenalidomide, the drug was administered without regard to food intake. Thus, lenalidomide can be administered with or without food.

Multiple dosing (up to 100 mg BID) did not cause marked drug accumulation.

b) Distribution – In vitro (^{14}C)-lenalidomide binding to plasma proteins is approximately 30%.

c) Metabolism – Lenalidomide undergoes limited metabolism. Unchanged lenalidomide is the predominant circulating component in humans. Two identified metabolites are hydroxy-lenalidomide and N-acetyl-lenalidomide; each constitutes less than 5% of parent levels in circulation.

d) Excretion – Elimination is primarily renal. Approximately 65% to 85% of lenalidomide is eliminated unchanged through urinary excretion in subjects with normal renal function. The half-life of elimination is approximately 3 to 4 hours (2 to 3 hours in patients 5 to 21 years) at the clinically relevant doses (5 to 50 mg/day). Steady-state levels are achieved within 4 days.

- 15.16 **Potential Drug Interactions:** In vitro studies demonstrate that lenalidomide is not a substrate of CYP enzymes. In addition, lenalidomide shows little inhibitory or induction potential towards the CYP enzymes in vitro. Hence, coadministration of CYP substrates, inhibitors, or inducers with lenalidomide is not likely to result in clinically relevant drug-drug interactions in humans.

In vitro, lenalidomide is not a substrate of BCRP, MRP1, MRP2, MRP3, OAT1, OAT3, OATP1B1, OCT1, OCT2, MATE1, OCTN1, or OCTN2. Thus, it is unlikely that substrates or inhibitors of these transporters would affect lenalidomide disposition in humans.

Lenalidomide is not an inhibitor of BSEP, BCRP, MRP2, OAT1, OAT3, OATP1B1, OATP1B3, or OCT2. Thus, lenalidomide is not anticipated to cause any significant drug-drug interactions due to inhibition of these transporters.

Lenalidomide is not an inhibitor of UGT1A1 and is not anticipated to cause any significant drug-drug interactions due to UGT1A1 inhibition.

In vitro, lenalidomide is a weak substrate, but not an inhibitor of P-glycoprotein (P-gp).

Erythropoietic agents or other agents that may increase the risk of thrombosis, such as hormone replacement therapy and oral contraceptives, should be used with caution in patients with multiple myeloma receiving lenalidomide with dexamethasone.

Periodic monitoring of digoxin plasma levels is recommended due to increased C_{max} and AUC with concomitant lenalidomide therapy. Close monitoring of PT and INR is recommended in multiple myeloma patients taking concomitant warfarin.

- 15.17 **Known potential toxicities:**

Pregnancy Warning: Lenalidomide, a thalidomide analogue, caused limb abnormalities in a developmental monkey study similar to birth defects caused by thalidomide in humans. If lenalidomide is used during pregnancy, it may cause birth defects or embryo-fetal death. Pregnancy must be excluded before start of

treatment. Prevent pregnancy during treatment by the use of two reliable methods of contraception.

Very Common AEs ($\geq 10\%$): anemia, leukopenia, neutropenia, thrombocytopenia, cataracts, blurred vision, abdominal pain, constipation, diarrhea, dyspepsia, nausea, vomiting, asthenia, chills, edema including peripheral, fatigue, pyrexia, abnormal liver function tests, bronchitis, nasopharyngitis, pneumonia, rhinitis, upper respiratory tract infection, urinary tract infection weight decreased, decreased appetite, hyperglycemia, hypocalcemia, hypokalemia, arthralgia, back pain, bone pain, muscle spasms, musculoskeletal pain, myalgia, pain in extremity, dizziness, dysgeusia, headache, hypoesthesia, neuropathy peripheral, neuropathy, tremor, depression, insomnia, cough, dyspnea, epistaxis, pharyngitis, pulmonary embolism, dry skin, pruritus, rash, and deep vein thrombosis.

Common ($\geq 1\%$ and $< 10\%$): febrile neutropenia, granulocytopenia, hemolytic anemia, lymphopenia, pancytopenia, acute myocardial infarction, atrial fibrillation, cardiac failure, congestive heart failure, myocardial ischemia, palpitations, tachycardia, vertigo, upper abdominal pain, dry mouth, toothache, chest pain, fall, cholestasis, bacteremia, erysipelas, gastroenteritis, herpes simplex, herpes zoster, influenza, lower respiratory infection, respiratory infection, sinusitis, sepsis, contusion, alanine aminotransferase increased, c-reactive protein increased, gamma-glutamyltransferase increased, dehydration, diabetes mellitus, gout, hyperuricemia, hypophosphatemia, hypomagnesemia, hyponatremia, iron overload, muscular weakness, acute myeloid leukemia, basal cell carcinoma, Myelodysplastic syndrome, squamous cell carcinoma of skin, tumor flare, tumor lysis syndrome, cerebrovascular accident, lethargy, paresthesia, peripheral sensory neuropathy, syncope, mood altered, renal failure, respiratory distress, erythema, hyperhidrosis, night sweats, hematoma, hypertension, hypotension, peripheral ischemia, thrombosis, and vasculitis.

Uncommon, limited to important or life-threatening ($< 1\%$): hypersensitivity, Graft vs. Host Disease

The following additional adverse reactions have been reported in Celgene-sponsored clinical studies and are considered by the company to be at least possibly related to the administration of lenalidomide: pneumonitis, transient abnormal liver laboratory tests, hyperthyroidism, TLS, TFR, rhabdomyolysis, and allergic conditions, including angioedema, SJS, and toxic epidermal necrolysis. These reactions are reported voluntarily from a population of uncertain size, so it is not possible to reliably estimate their frequency.

Lenalidomide may have minor or moderate influence on the ability to drive and use machines. Fatigue, dizziness, somnolence, vertigo and blurred vision have been reported with the use of lenalidomide. Therefore, caution is recommended when driving or operating machines.

Please refer to the Investigator's Brochure for a more comprehensive list of treatment-emergent adverse events.

- 15.18 **Drug procurement:** Lenalidomide (Revlimid®) will be provided directly to research subjects for the duration of their participation in this trial at no charge to them or their insurance providers in accordance with the REVLIMID REMS™ program. Per standard requirements all physicians who prescribe lenalidomide for research subjects enrolled into this trial, and all research subjects enrolled into this trial, must be registered in and must comply with all requirements of the Celgene REVLIMID REMS™ program. Prescriptions must be filled within 7 days. Consideration should be given to prescribing lenalidomide 5 to 7 days in advance of Day 1 of each cycle to allow time for required patient and prescriber surveys, and drug shipment to patient. **Only enough lenalidomide for one cycle of therapy will be supplied to the patient each cycle.**

Further information about the Revlimid REMS™ program is available at

Outdated or remaining drug is to be destroyed on-site as per procedures in place at each institution.

15.19 **Nursing Guidelines:**

- 15.191 Myelosuppression is dose-dependent and reversible with treatment interruption and/or dose reduction. Monitor CBC w/diff regularly. Instruct patient to report any unusual bruising or bleeding (thrombocytopenia); signs and symptoms of infection (neutropenia); and energy conserving lifestyle (anemia).
- 15.192 Lenalidomide can have thrombotic adverse events (i.e DVT and PE). Instruct patient to report any limb swelling or pain, and to seek medical attention for shortness of breath or chest pain.
- 15.193 Because of the potential for birth defects patients should be instructed in effective methods of birth control. Female patients should use 2 forms of birth control during treatment and for 4 weeks after discontinuing therapy. Males must be instructed to use a latex condom during any sexual contact with a woman of child bearing potential (even if they have had a vasectomy), because it is unknown if lenalidomide is present in semen.
- 15.194 Patients may experience pruritus, rash and dry skin. Because of the rare risk of Steven's Johnson Syndrome, patients should immediately report any rash to their provider.
- 15.195 Drug may cause hyperglycemia. Patients with diabetes or impaired fasting glucose may need to have their glucose levels monitored more closely.
- 15.196 Gastrointestinal side effects (diarrhea, constipation, nausea, dyspepsia, anorexia, etc) are commonly seen. Manage patient symptomatically and monitor for effectiveness.
- 15.197 Patients may experience myalgias, arthralgias, and other generalized pain. Administer analgesics as ordered and monitor for their effectiveness.
- 15.198 Upper respiratory symptoms (nasopharyngitis, cough, epistaxis, etc.) can be seen. Manage symptomatically and monitor for effectiveness.

15.199 Agent may cause fatigue, dizziness, vertigo or blurred vision. Instruct patients to use caution when driving or operating machines.

